9.3.1 Return and Retention of Study Drug

Remaining drug is to be destroyed, according to Moores Cancer Center Investigational Drug Services destruction policy or the institutional policy of the individual participating institutions. Drug accountability and record of drug destruction must be provided to UCSD BMT Clinical Trials Office.

10. STATISTICAL CONSIDERATIONS

10.1 Study Design/Study Endpoints

This is a Phase I/II single-arm, open-label, multicenter study of pembrolizumab in combination with blinatumomab. This study includes a Phase I safety run-in of 3-6 patients followed by accrual of 18-21 additional patients for a total of 24.

10.2 Sample Size and Accrual

Patients presenting to outpatient clinics and inpatient settings or existing patients at participating sites with relapsed or refractory B-lineage ALL will be approached by treating providers or their representatives regarding interest in trial participation.

The accrual goal is 24 patients. Rationale for accrual goal is outlined in **Section 10.5.1**

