10.4 Evaluable Subjects and Subject Replacement

Stage 1 (Safety evaluation)

Evaluable subjects are defined as any patient receiving the combination of blinatumomab and pembrolizumab starting day 15 of Cycle 1. The DLT monitoring period will be 28 days starting Day 15 of Cycle 1. Subjects withdrawing from investigational treatment during the 28 day DLT monitoring period for a reason that is definitely unrelated to toxicity of the study agent (e.g. disease progression, patient withdrawal of consent) will be replaced for the safety analysis. 3-6 patients will be enrolled at in Stage 1 as determined by 3+3 rules. These patients will also be evaluated for efficacy.

Stage 2

Stage 2 of the study will include an expansion cohort of up to 21 additional subjects for a total of 24 subjects to evaluate the efficacy of the combination of blinatumomab and pembrolizumab. All patients receiving combination therapy starting day 15 of cycle 1 will be considered evaluable for overall response rate of entire population, RFS and OS.

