10.5 Data Analyses Plans

10.5.1 Primary Analysis

Simon's 2-stage for efficacy

We plan a Simon's 2-stage MiniMax design evaluation of the combination of blinatumomab and pembrolizumab in relapsed or refractory B-cell ALL with >50% blasts in the marrow.

We assessed the sample size for studying using overall response rate (CR + CRh). From recent large Phase II study including 189 subjects with relapsed/refractory B-lineage ALL, ORR (CR + CRh) to blinatumomab monotherapy was approximately 29% in patients with >50% lymphoblasts in the bone marrow (Topp et al. 2015). Response rates for PD-1 inhibitors in relapsed or refractory ALL are unknown but given mechanism of action it likely approaches zero.

An absolute increase in the overall response rate of 25 percentage points (i.e. to 54% ORR in patients evaluable for efficacy) or greater will demonstrate sufficient activity to consider the regimen for further study.

To calculate sample sizes for Stage 1 and Stage 2 we used a probability of type I error (α) = 0.05 and a power ($1-\beta$) = 0.80 with $p_0=0.29$ and $p_1=0.54$.

The null hypothesis that the true response rate is 0.29 will be tested against a one-sided alternative. In the first stage, 18 patients evaluable for efficacy will be accrued. If there are 7 or fewer responses in these 18 patients, the study will be stopped. Otherwise, 6 additional patients will be accrued for a total of 24 patients evaluable for efficacy of the combination. The null hypothesis will be rejected if 11 or more responses are observed in 24 evaluable patients. This design yields a type I error rate of 0.05 and power of 0.80 when the true response rate is 0.54. The likelihood of early termination is 0.88, if the null hypothesis is true.

Safety rules

At the time of the Stage 1 efficacy analysis, all patients will be reviewed again for DLTs as defined in Section 5.1.4 occurring at any time during therapy.

A DLT rate exceeding 0.3 will be considered unacceptable. The first 3, 6, 12, and 24 patients will be monitored for DLTs. The first 6 patients will be monitored every other week. The next 6 patients will be monitored monthly. Subsequent patients will be monitored every other month.

k	1	2	3	4
n_k	3	3	6	12

N_k	3	6	12	24
r_k	1	1	3	5

Table: Monitoring design for DLTs. The stage is denoted by k . The number of patients accrued during and up to stage k are denoted by n_k and N_k respectively. The critical value at stage k is denoted by r_k .

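### The plan sets 24 subjects enrolled, but the 11-of-24 rule and the 0.80 power need 24 evaluable for efficacy, and no rule covers any other number.

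*Combined protocol and SAP*

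**What the plan says.** **Total number of subjects.** Section 10.2 states "The accrual goal is 24 patients" and refers to Section 10.5.1 for the rationale. Section 10.1 describes a run-in of 3–6 patients and then "accrual of 18-21 additional patients for a total of 24". Section 5.1.5 says that 24 in total will be enrolled, and Section 10.3 labels its table, with a total of 24, as maximum accrual. The study summary and Sections 5.1.1 and 10.4 give the same total.

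**The test.** Section 10.5.1: "We plan a Simon's 2-stage MiniMax design evaluation of the combination of blinatumomab and pembrolizumab". On the hypothesis it says: "The null hypothesis that the true response rate is 0.29 will be tested against a one-sided alternative". The futility look is then set out as follows: "In the first stage, 18 patients evaluable for efficacy will be accrued"; seven or fewer responses stop the study. Otherwise "6 additional patients will be accrued for a total of 24 patients evaluable for efficacy of the combination", and 11 or more responses in 24 evaluable patients reject the null. The operating characteristics are given as: "This design yields a type I error rate of 0.05 and power of 0.80 when the true response rate is 0.54".

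**Who is evaluable.** Section 10.4: "All patients receiving combination therapy starting day 15 of cycle 1 will be considered evaluable for overall response rate of entire population". Section 7.1.1 asks for more: at least one cycle of therapy and a repeat disease assessment.

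**Replacement.** Sections 5.1.1, 5.1.4 and 10.4 replace subjects who leave during the DLT window for reasons unrelated to toxicity. This serves the safety evaluation only. No section replaces a patient who is not evaluable for efficacy.

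**The concern.** The enrolment total and the number that the decision rule needs are both 24, but they count different people. A patient can enrol and never become evaluable: blinatumomab is given alone for the first 14 days, and Section 5.7.1 has toxicity rules that end protocol therapy, which can apply in that period. Each such loss leaves fewer than 24 evaluable unless enrolment goes above 24, and the plan states no cut-off for another number.

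Two things are at stake. The stated power would not apply to the trial as enrolled. The final cut for the primary endpoint would also have to be chosen in an open-label study with the responses already known, and the obvious choice of dropping to 10 exceeds the 0.05 error rate.

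**Working it through.** **Inputs (Section 10.5.1).** p0 = 0.29, p1 = 0.54, one-sided alpha 0.05, power 0.80; first look at 18 evaluable, stop at 7 or fewer; reject at 11 or more of 24 evaluable. The number of non-evaluable patients is not in the documents; one to three is an assumption.

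**Formula.** With X1 ~ Bin(18, p) and X2 ~ Bin(n − 18, p), independent:

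P(reject) = Σ over x = 8, 9, 10 of P(X1 = x) · P(X2 ≥ 11 − x) + P(X1 ≥ 11).

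**1. The plan's own figures, n = 24.**
- At p = 0.29: 0.07126 × 0.2374 + 0.03234 × 0.5580 + 0.01189 × 0.8719 + 0.00456 = 0.0499. P(X1 ≤ 7) = 0.880.
- At p = 0.54: 0.1342 × 0.7279 + 0.1751 × 0.9238 + 0.1850 × 0.9905 + 0.3588 = 0.8014. P(X1 ≤ 7) = 0.147.

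The stated 0.05, 0.80 and 0.88 all reproduce. A full search over two-stage designs with up to 24 patients finds this one (7/18, then 11/24) as the only design that meets both constraints, so it has no slack.

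**2. Fewer evaluable, losses after the first look.** First look kept at 18 with bound 7, final cut kept at 11. For n = 23, power is 0.1342 × 0.5747 + 0.1751 × 0.8585 + 0.1850 × 0.9794 + 0.3588 = 0.767. In the same way:

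| Evaluable n | Alpha | Power |
|---|---|---|
| 24 | 0.0499 | 0.801 |
| 23 | 0.040 | 0.767 |
| 22 | 0.030 | 0.716 |
| 21 | 0.021 | 0.645 (0.6449) |

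**3. Fewer evaluable, losses before the first look.** If the look is taken at 17, 16 or 15 with the bound of 7 kept, and the totals are 23, 22 and 21, power is 0.733, 0.650 and 0.553.

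**4. Lowering the final cut to 10** (first look at 18). At n = 23, 22 and 21, alpha is 0.075, 0.064 and 0.052, all above 0.05.

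**5. More than 24 evaluable, first look at 18.** Keeping 11 gives alpha 0.060 at n = 25 and 0.069 at n = 26. A cut of 12 gives alpha 0.031 and 0.039, with power 0.760 and 0.794.

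**6. Twenty evaluable, first look at 18.** A cut of 10 gives alpha 0.038 and power 0.721.

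**7. How likely is any loss?** If each of 24 patients has probability q of being non-evaluable, P(at least one loss) = 1 − (1 − q)^24. For assumed q of 0.02, 0.05 and 0.10 this is 0.38, 0.71 and 0.92.

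**The case against.** The strongest reply is that Section 10.2 defers to Section 10.5.1, which counts accrual in evaluable patients. On that reading enrolment continues until 24 are evaluable, and the rule, the alpha and the power all hold. This stands as a possible reading of those two sections. It does not settle the matter, because Section 5.1.5 speaks of 24 enrolled and Section 10.3 calls 24 the maximum.

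A reader might infer that the final analysis will very likely have a number for which the plan has no rule. The documents do not support that. They give no non-evaluable rate, and step 7 runs from 0.38 to 0.92 on assumed rates alone. Sections 5.1.3 and 5.8 remove patients for progression only after Day 15 of Cycle 1, so early progression is not by itself a listed reason to miss the Section 10.4 threshold. Under the null the trial also stops at 18 with probability 0.88.

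A reader might also infer that the sample-size calculation is wrong. It is not; every stated figure reproduces.

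Finally, the power loss and the inflated alpha at 25 or 26 need different premises. More than 24 evaluable can arise only if 24 is not a hard cap.

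Counting non-evaluable patients as non-responders in a denominator of 24 does not avoid the power loss: the 11 responses must still come from 21 to 23 patients.

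**Conclusion.** The concern holds as an inconsistency between enrolled and evaluable numbers, together with a missing rule for an attained number other than 24. The stated power of 0.80 applies only at 24 evaluable. On the assumption of one, two or three losses among 24 enrolled, with 18 evaluable still reached at the first look and the cut kept at 11, it falls to 0.77, 0.72 or 0.64. It falls to 0.73, 0.65 or 0.55 if the losses come out of the first look with its bound unchanged. Type I error is not inflated by losses if the cut stays at 11; it is inflated if the cut is lowered to 10 at 21–23, or kept at 11 at 25 or 26. How many patients would be lost cannot be judged from the documents. The two definitions of evaluable make even the attained number uncertain until they are reconciled.

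**What to change.** 1. In Sections 5.1.5, 10.1, 10.2 and 10.3, state whether 24 means enrolled or evaluable for efficacy, and align the study summary and Sections 5.1.1 and 10.4.
2. Use one definition of evaluable for efficacy in Sections 7.1.1 and 10.4.
3. If 24 means enrolled, say in Section 10.5.1 that power of 0.80 applies only at 24 evaluable, and give 0.77, 0.72 and 0.64 for 23, 22 and 21.
4. In either case, prespecify in Section 10.5.1 that the first look is at 18 evaluable, and give the final cut for the attained number:

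| Evaluable n | Reject at or above | Alpha | Power |
|---|---|---|---|
| 20 | 10 | 0.038 | 0.721 |
| 21 | 11 | 0.021 | 0.645 |
| 22 | 11 | 0.030 | 0.716 |
| 23 | 11 | 0.040 | 0.767 |
| 24 | 11 | 0.0499 | 0.801 |
| 25 | 12 | 0.031 | 0.760 |
| 26 | 12 | 0.039 | 0.794 |

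Power does not rise steadily with n because the cut moves in whole responses; the table should say so.

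**Cost.** Wording and one table. The stated power becomes less favourable if fewer than 24 are evaluable. The fix itself requires no extra patients; if the sponsor decides that 24 means evaluable, enrolment may exceed 24 by the number lost.

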10.3 Enrollment targets by race/ethnicity and sex

Accrual Targets (for maximum accrual)			
Ethnic Category	Sex/Gender		
	Females	Males	Total
Hispanic or Latino	4	5	9
Not Hispanic or Latino	6	9	15
Ethnic Category: Total of all subjects	10	15	24
Racial Category			
American Indian or Alaskan Native	0	0	0
Asian	1	1	2
Black or African American	1	1	2
Native Hawaiian or other Pacific Islander	0	0	0
White	9	11	20
Racial Category: Total of all subjects	11	14	24

10.4 Evaluable Subjects and Subject Replacement

Stage 1 (Safety evaluation)

Evaluable subjects are defined as any patient receiving the combination of blinatumomab and pembrolizumab starting day 15 of Cycle 1. The DLT monitoring period will be 28 days starting Day 15 of Cycle 1. Subjects withdrawing from investigational treatment during the 28 day DLT monitoring period for a reason that is definitely unrelated to toxicity of the study agent (e.g. disease progression, patient withdrawal of consent) will be replaced for the safety analysis. 3-6 patients will be enrolled at in Stage 1 as determined by 3+3 rules. These patients will also be evaluated for efficacy.

Stage 2

Stage 2 of the study will include an expansion cohort of up to 21 additional subjects for a total of 24 subjects to evaluate the efficacy of the combination of blinatumomab and pembrolizumab. All patients receiving combination therapy starting day 15 of cycle 1 will be considered evaluable for overall response rate of entire population, RFS and OS.

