5. TREATMENT PLAN

5.1 Treatment dosage and administration

5.1.1 Treatment summary

The study will be conducted in 2 stages:

Stage 1 is to ensure safety of pembrolizumab in combination with blinatumomab.

Dose Limiting Toxicity (DLT) is defined as a clinically significant adverse event that is considered by the investigator to be probably or definitely related to pembrolizumab or the combination of pembrolizumab and blinatumomab occurring within 42 days of the first dose of pembrolizumab on Day 15 of Cycle 1 as follows:

- Any Grade 3-5 non-hematologic toxicity EXCEPT:
 - Grade 3 cytokine release syndrome that resolves in 7 days or less
 - Grade 3 neurotoxicity that resolves in 7 days or less
 - Grade 3 infections
 - Grade 3 or 4 febrile neutropenia unless deemed by investigator to be definitely related to pembrolizumab
 - Grade 3 or 4 laboratory abnormalities unless they warrant temporary discontinuation of pembrolizumab or permanent discontinuation of blinatumomab (see tables, 5.7.1 and 5.7.2)
 - Grade 3 or 4 lymphopenia
- Any clinically significant toxicity that precludes administration of the next scheduled dose for more than 14 days

If no DLTs are experienced in the first 3 subjects then enrollment will advance Stage 2. If 1 DLT is noted in the first 3 subjects then 3 additional subjects will be enrolled. If no further DLTs are noted in the additional 3 subjects then enrollment will proceed to Stage 2. If 2 or more DLTs are noted at the proposed pembrolizumab dose level and schedule then enrollment will be placed on hold and a dose reduction or schedule change will be considered after discussion of investigators.

The DLT monitoring period will be 42 days starting on Day 15 of Cycle 1. Subjects withdrawing from investigational treatment during the DLT monitoring period for a reason that is definitely unrelated to toxicity of the study agent (e.g. disease progression, patient withdrawal of consent) will be deemed not evaluable for DLT determination and will be replaced. All subjects in Stage 1 will need to complete the DLT monitoring period prior to proceeding with Stage 2.

Stage 2 of the study will include an expansion cohort of up to 21 additional subjects (for a total of 24 subjects) to evaluate the efficacy of the combination of blinatumomab and pembrolizumab.

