5.1.3 Therapy

[figure not shown]
Both Stage 1 (safety lead-in) and Stage 2 (dose expansion) of this study will use the same regimen as detailed below.

Schema:

Cycle 1

Cycle 2-5

REGIMEN DESCRIPTION					
CYCLE 1					
Agent	Premedications; Precautions	Dose	Route	Schedule	Cycle Length
Blinatumomab	Dexamethasone 20 mg IV once 1 hour (+/- 30 min) before start of infusion and 1 hour (+/- 30 min) prior to step-up dose on Day 8.	Day 1-7: 9 mcg/day	Continuous IV infusion for 28 days. Bag changes every, 24 hours, 48 hours or 7 days (as appropriate).	Day 1-7	6 weeks (42 days)
		Day 8-28: 28 mcg/day		Day 8-28	
Pembrolizumab	None required, per institutional	200 mg	IV over 30 minutes	Days 15 and 36	

	standard of care				
Methotrexate	None required, per institutional standard of care	15 mg	Intrathecal or intraventricular	Day 29 + 8 days	
CYCLES 2-5					
Blinatumomab	Dexamethasone 20 mg IV once 1 hour (+/- 30 min) before start of infusion.	28 mcg/day	Continuous IV infusion for 28 days. Bag changes every 24hours, 48 hours or 7 days (as appropriate).	Days 1-28	6 weeks (42 days)
Pembrolizumab	None required, per institutional standard of care	200 mg	IV over 30 minutes	Days 15 and 36	
Methotrexate	None required, per institutional standard of care	15 mg	Intrathecal or intraventricular	Day 29 + 8 days	

See **Section 9.1** for details on administration of blinatumomab

Hospitalization requirements:

Cycle 1:

Hospital admission required from day 1 through day 18 and for at least 72 hours after pembrolizumab dose.

Cycle 2:

Hospital admission required day 1-3 for blinatumomab and for at least 72 hours after start of blinatumomab infusion.

Cycles 3-5:

Hospital admission required day 1-3 for blinatumomab and for at least 72 hours after start of blinatumomab infusion.

Hospital admission also required for any blinatumomab restart or step-dose increase and for 72 hours after restart or step-up dose.

Vital signs (heart rate and oxygen saturation) to be monitored continuously and full vital signs (temperature, heart rate, blood pressure, respiratory rate, and oxygen saturation) every 4 hours

during at least the initial 72 hours of blinatumomab therapy, for 72 hours after all restart or step-up doses, and for at least the initial 72 hours following the first (Cycle 1, Day 15) pembrolizumab doses.

CNS Prophylaxis:

Methotrexate 15mg intrathecal or intraventricular at screening, day 29 + 8 days of cycle 1-4, and day 38 +8 days of cycle 5 (end of treatment)

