5.7 Toxicities and Dosing Delays/Dose Modifications

Any patient who receives treatment on this protocol will be evaluable for toxicity. Each patient

will be assessed for the development of toxicity except cytokine release syndrome (see below, grading/management per Lee et al. Blood 2014) according to the NCI Common Toxicity Criteria for Adverse Events (CTCAE), version 4.03. Dose adjustments should be made according to the system showing the greatest degree of toxicity. As Blinatumomab is an approved treatment for this indication, reducing or withholding pembrolizumab should be considered as the first option in response to a toxicity prior to adjusting the Blinatumomab dosing.

Adverse events (both non-serious and serious) associated with pembrolizumab exposure may represent an immunologic etiology. These adverse events may occur shortly after the first dose or several months after the last dose of treatment. Pembrolizumab and blinatumomab must be withheld for drug-related toxicities and severe or life-threatening AEs as per Tables below. See Section 5.6.1 in Events of Clinical Interest Guidance Document for additional supportive care guidelines.

All dose adjustments presume that the toxicity is determined by the investigator to be possibly, probably, or definitely related to blinatumomab, pembrolizumab, or both. Withholding the dose and dose adjustments should not occur if toxicity is felt unlikely to be or definitely not related to study blinatumomab, pembrolizumab, or both.

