Grade 4 -Mechanical ventilation -Organ toxicity: Grade 4 excluding transaminitis	Off protocol therapy. Vigilant supportive care. Assess for infection. Consider administration of corticosteroids and/or tocilizumab..	Off protocol therapy. Vigilant supportive care. Assess for infection. Consider administration of corticosteroids and/or tocilizumab..

*Patients requiring a delay of blinatumomab >14 days should go off protocol therapy.
 
**High-dose pressors include the following administered for ≥3 hours: norepinephrine ≥20 mcg/min, dopamine ≥10 mcg/kg/min, phenylephrine ≥200 mcg/min, epinephrine ≥10 mcg/min, if on vasopressin: vasopressin + norepinephrine equivalent of ≥10 mcg/min, if on combination of vasopressors: norepinephrine equivalent ≥20 mcg/min. NOREPINEPHRINE EQUIVALENT DOSE = [norepinephrine (mcg/min)] + [dopamine (mcg/kg/min)/2] + [epinephrine (mcg/min)] + [phenylephrine (mcg/min)/10]/
		

Neurologic Toxicity	Management for Blinatumomab	Management for Pembrolizumab
Grade 1 or 2	Continue infusion.	No change in dose.
Grade 3	Withhold* until < Grade 2 for 3 days then resume blinatumomab at 9 mcg/day. Escalate to 28 mcg/day after 7 days if the toxicity does not recur. If the toxicity occurred at 9 mcg/day or takes more than 7 days to improve to <Grade 2 then patient goes off protocol therapy.	Withhold* until < Grade 2 then resume at same dose. Missed doses should be given as close to missed scheduled dose as possible. Subsequent doses are given every 3 weeks.
Grade 4	Off protocol therapy	Off protocol therapy
Seizure, Grade 1 or 2	Withhold* until resolved and institute anticonvulsant prophylaxis (neurology consultation)	Withhold until resolved then resume at same dose. Missed doses should be given as close to

Neurologic Toxicity	Management for Blinatumomab	Management for Pembrolizumab
	recommended) then resume blinatumomab at 9 mcg/day. Escalate to 28 mcg/day after 7 days if the toxicity does not recur.	missed scheduled dose as possible. Subsequent doses are given every 3 weeks until completion of planned cycles of therapy.
Seizure, Grade 3 or 4 or recurrent Grade 1 or 2	Off protocol therapy.	Off protocol therapy.
*Patients requiring a delay of blinatumomab >14 days should go off protocol therapy.		

Infusion Reactions	Management for Blinatumomab	Management for Pembrolizumab
≤ Grade 1	Refer to CRS section above.	Increase monitoring of vital signs as needed until clinical stability confirmed. No change in dose.

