Grade 4	Permanently discontinue blinatumomab.	Give methylprednisolone 2 mg/kg IV once then prednisone 1-2 mg/kg oral daily with taper over at least 4 weeks after resolution to ≤ Grade 1. Permanently discontinue pembrolizumab.
*Patients requiring a delay of blinatumomab > 14 days due to toxicity should go off protocol therapy.		

Other Non-Hematologic Adverse Reactions Despite Optimal Supportive Care	Management for Blinatumomab	Management for Pembrolizumab
Grade 1 or 2	Continue infusion.	No change in dose
Grade 3	Withhold* until < Grade 2 then resume blinatumomab at 9 mcg/day. Escalate to 28 mcg/day after 7 days if the toxicity does not recur. If Grade 3 toxicity recurs despite optimal supportive care, permanently discontinue blinatumomab.	Withhold* until < Grade 2 then resume at same dose. Missed doses are not made up. If Grade 3 toxicity recurs despite optimal supportive care, permanently discontinue pembrolizumab.
Grade 4	Permanently discontinue blinatumomab.	Permanently discontinue pembrolizumab.
*Patients requiring a delay of next cycle by >14 days due to toxicity should go off protocol therapy.		

For additional toxicity management guidance please reference Brahmer et al, “Management of immune-related adverse events in patients treated with immune checkpoint inhibitor therapy: ASCO clinical practice guideline” in JCO Feb 2018; the NCCN guidelines for “Management of Immunotherapy-related toxicities”); and the SITC guidelines by Puanov et al, “Managing toxicities associated with immune checkpoint inhibitors: consensus recommendations from the SITC toxicity management working group” in JITC Nov 2017.

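### The run-in DLT period and Stage 1 evaluability are tied to Cycle 1 Day 15, with no rule for a patient whose first pembrolizumab dose is held past that day

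*Combined protocol and SAP*

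**What the plan says.** Three elements of the run-in each refer to Day 15, in different ways.

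- **DLT definition (5.1.1, repeated in 5.1.4).** Events count when "occurring within 42 days of the first dose of pembrolizumab on Day 15 of Cycle 1 as follows". This names the first dose and assumes its date.
- **Monitoring period.** Section 5.1.1: "The DLT monitoring period will be 42 days starting on Day 15 of Cycle 1". Section 10.4: "The DLT monitoring period will be 28 days starting Day 15 of Cycle 1". Both are calendar-fixed, and they differ in length. Section 5.1.1 requires all Stage 1 subjects to complete the period before Stage 2 proceeds.
- **Stage 1 evaluability (10.4).** "Evaluable subjects are defined as any patient receiving the combination of blinatumomab and pembrolizumab starting day 15 of Cycle 1".

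Replacement (5.1.1, 5.1.4, 10.4) covers only subjects who withdraw from treatment during the period for a reason definitely unrelated to toxicity.

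Section 5.1.3 schedules pembrolizumab on Days 15 and 36 of each 42-day cycle. Blinatumomab is a "Continuous IV infusion for 28 days" from Day 1, so patients have 14 days of blinatumomab, including the Day 8 step-up, before the first pembrolizumab dose. The adjustment rules in 5.7 cover toxicity from either drug: "All dose adjustments presume that the toxicity is determined by the investigator to be possibly, probably, or definitely related to blinatumomab, pembrolizumab, or both". The tables in 5.7.1 then treat a missed pembrolizumab dose in two ways. For other non-hematologic Grade 3 events: "Withhold* until < Grade 2 then resume at same dose. Missed doses are not made up". For Grade 3 neurologic toxicity: "Missed doses should be given as close to missed scheduled dose as possible".

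**The concern.** The run-in rules assume that the first pembrolizumab dose is given on Day 15, but the plan's own toxicity rules allow it to be later. Once it is late, the definition of a DLT, the period over which the patient is watched and the test of evaluability no longer describe the same interval, and no section says which governs.

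The run-in has only 3 to 6 patients, so the handling of one patient can change the decision to open Stage 2. If the calendar sentence is applied, a patient could count as having completed monitoring after a fraction of the intended exposure. If the evaluability sentence is applied, the cohort is one patient short with no rule to refill it. The hold itself would not count as a DLT, because a DLT must be probably or definitely related to pembrolizumab or to the combination.

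**Working it through.** **Inputs.** Pembrolizumab on Days 15 and 36, blinatumomab on Days 1-28 of each cycle, 42-day cycles (5.1.3). Window length W = 42 (5.1.1) or 28 (10.4), starting Day 15. Decision rule from 5.1.4: proceed on 0 of 3 DLTs, or on 1 of 3 followed by 0 of 3. A DLT rate above 0.3 is unacceptable (10.5.1). The plan gives no operating characteristics for the run-in, so there is no stated figure to reproduce.

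**Step 1: day counts.** With Cycle 1 Day 1 as Day 1, Cycle 2 Day 1 is Day 43. Window end = 15 + W - 1, which is Day 56 for W = 42 and Day 42 for W = 28. Days from first dose to window end = end - first dose day + 1. Concurrent blinatumomab days are planned days, assuming the infusion runs to schedule.

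| First pembrolizumab dose | 42-day window: days observed / planned concurrent blinatumomab days | 28-day window: same |
|---|---|---|
| Day 15 (as planned) | 42 / 28 | 28 / 14 |
| Day 22 | 35 / 21 | 21 / 7 |
| Day 36 | 21 / 14 | 7 / 0 |

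A Day 36 starter receives one pembrolizumab dose in the 42-day window instead of two, because the next dose is Cycle 2 Day 15, which is Day 57.

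**Step 2: the three outcomes for a Day 36 starter.**

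1. Calendar period applied: monitoring is complete on Day 56 (5.1.1) or Day 42 (10.4), with 21 or 7 days from first dose. These are two values from two conflicting windows, not the ends of a range.
2. Evaluability sentence read literally: the combination did not start on Day 15, so the patient is not evaluable. The patient has not withdrawn, so is not replaced.
3. DLT definition read from the actual first dose: events count to 36 + 42 - 1 = Day 77, which is 21 days after the 42-day monitoring period has closed.

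**Step 3: illustration of outcome 1.** Assume a constant DLT hazard, full-window DLT probability p, one of the first three patients observed for only part of the window, and the others observed in full. That patient's chance of an observed DLT is q = 1 - (1 - p)^(days observed / W). The probability of clearing the run-in is

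C = (1 - q)(1 - p)² + [q(1 - p)² + 2(1 - q)p(1 - p)](1 - p)³.

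At p = 0.3:

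- Full observation (q = p): 0.343 + 0.441 × 0.343 = 0.494.
- 21 of 42 days: q = 1 - 0.7^0.5 = 0.163. C = 0.410 + (0.080 + 0.351) × 0.343 = 0.558.
- 7 of 28 days, taking 0.3 as the 28-day rate: q = 1 - 0.7^0.25 = 0.085. C = 0.448 + (0.042 + 0.384) × 0.343 = 0.594.
- 35 of 42 days (first dose on Day 22): q = 1 - 0.7^(35/42) = 0.257. C = 0.364 + (0.126 + 0.312) × 0.343 = 0.514.

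For 21 of 42 days, clearance rises from 0.709 to 0.754 at p = 0.2 and from 0.309 to 0.377 at p = 0.4.

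**The case against.** - **The definition already refers to the first dose.** This is correct. The drafters treated Day 15 and the first dose as the same date, so a reader who infers that the plan ignores the first dose goes too far. The conflict remains, because the monitoring period and the Stage 2 gate use the calendar date only.
- **A reader might infer that a late starter will be cleared after 7 to 21 days.** The documents do not support that. Clearance is one of three readings, and 10.4 taken literally makes the patient not evaluable, which is the opposite of cleared.
- **The route to Day 36 is narrow.** This stands. Grade 1-2 cytokine release syndrome leaves pembrolizumab unchanged, and Grades 3 and 4 end trial treatment, so neither produces a late start. Grade 3 neurologic toxicity that takes more than 7 days to improve below Grade 2, or that arose at the starting blinatumomab dose, takes the patient off protocol. Otherwise the missed dose is given late, by about Day 22 for a hold beginning around Day 15, and the effect is small (0.494 to 0.514). Day 36 arises only under rows that do not make up missed doses.
- **Later events are not lost.** Section 10.5.1 monitors the first 3, 6, 12 and 24 patients for DLTs, the first 6 every other week, with limits that suspend enrollment. It reviews all patients again at the Stage 1 efficacy analysis. This is a real safeguard, but it does not define when the run-in is complete, and that later review comes after 18 evaluable patients.
- **The same Day 15 wording appears in the Stage 2 part of 10.4.** One might be tempted to rewrite it too. That would change the denominator for response, RFS and OS, and nothing here supports doing so.

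**Conclusion.** The plan has an unresolved conflict in the rule that opens Stage 2. It matters only when a run-in patient's first pembrolizumab dose is delayed, and in that case the documents allow three incompatible treatments of the same patient. At the extreme, a Day 36 start leaves 21 of 42 days of observation, or 7 of 28 with no planned concurrent blinatumomab.

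The rise in run-in clearance from 0.49 to 0.56 rests on an assumed constant hazard, a 42-day DLT rate of 0.3, exactly one such patient among the first three, and the calendar reading. The documents give no frequency for Day 15 holds, so the probability that this happens is not estimated. A reader might conclude that the run-in will pass an unsafe combination. The evidence supports only that the gate is undefined for this patient and that one of its readings is lenient.

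**What to change.** In 5.1.1, 5.1.4 and the Stage 1 part of 10.4:

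- Start the DLT period on the date of the first pembrolizumab dose, whenever it is given, and use the same start date in the DLT definition and the monitoring-period sentence.
- Count a Stage 1 subject as DLT-free only after the full period from that date.
- Base Stage 1 evaluability on having received the combination rather than on starting on Day 15. State what counts as receiving it, since Day 36 falls in the part of the cycle with no planned blinatumomab.
- Reconcile the 28-day and 42-day period lengths. The sponsor must decide which applies.

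Leave the Stage 2 efficacy-evaluability wording in 10.4 out of this change. No dose or withholding rule needs to change.

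The cost is wording in three sections. If a run-in patient starts on Day 36, the period ends on Day 77 instead of Day 56 (42 days) or Day 63 instead of Day 42 (28 days), so Stage 2 could open up to about 3 weeks later.
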